3.3.2 Demographic and baseline characteristics

Demographic and baseline characteristics are collected at screening. Descriptive summaries will be provided. The number and percentages (categorical variables) and descriptive statistics (continuous variables) will be summarized for the following:

Demographic

- Age (years), age group (≥ 18 to < 65 years, ≥ 65 to < 75 years, ≥ 75 years)
- Gender (Male, Female)
- Height (m)
- Weight (kg)
- BMI (kg/m^2)
- BMI Category (18.5 to < 25 , 25 to < 30 , ≥ 30)

Refer to section 0 for derivations.

Disease characteristics

- Leg of target wound (Right, left, both)
- Primary ambulatory method (Walks unaided, cane, crutches, walker, roll about, scooter, wheelchair bound, bed bound)
- Take pain medication regularly? (Yes, No)

Additionally, the following information will be summarized for each target wound:

- Received grafting for target wound? (Yes, No)
- Hospitalization for target wound? (Yes, No)
- Duration of compression therapy at baseline on current target wound (weeks)
- Compliance with compression at baseline? (Yes, No)
- Previous procedures/treatments for target wound? (Yes, No)
- If yes to previous procedure/treatment, outcome of previous treatments (Healed, Not healed)
- Whether target wound is circumferential (Yes, No)
- Wound age at first encounter (weeks)
- Total wounds or ulcers
- Number of previous ulcers
- Signs of infection or bioburden indicated by exudate (Yes, No)

Venous characteristics

The following will be summarized for each target wound:

- Duplex reflux (milliseconds)
- GSV incompetence? (Yes, No)
- AASV incompetence? (Yes, No)
- Major perforator incompetence? (Yes, No)
- Small Saphenous Vein (SSV) incompetence? (Yes, No)
- Peripheral arterial disease? (Yes, No)

3.3.3 Protocol deviations

Protocol deviations/violations not related to the informed consent process or eligibility are not required to be reported to Sponsor for this registry. Protocol deviations related to informed consent or eligibility are tracked outside of the electronic data capture and will be provided in an Excel sheet as the source. The number and percentage of patients with protocol deviations will be summarized.

3.4 Treatment and other medication and therapies

3.4.1 Study treatment

The following index treatment analyses will be summarized by target wound:

- Total injection sites
- Volume injected above the knee (mL)
- Volume injected below the knee (mL)

The number of patients with additional treatment will be summarized. Additionally, the number of additional treatments will also be summarized by wound along with the following:

- Leg (Right, left)
- For target wound? (Yes, no)

- Duration (days) from date of first treatment to the start of an additional treatment
 - $Duration\ (days) = date\ of\ additional\ Varithena\ treatment - date\ of\ first\ Varithena\ treatment + 1$
- Total injection sites
- Volume injected above the knee (mL)
- Volume injected below the knee (mL)

The number of additional treatments will be further split into the number of additional Varithena treatments and the number of adjunctive treatments. Adjunctive treatments are defined as the volume above the knee and below the knee are both 0 mL.

The following treatment analyses will be summarized by visit time point:

- Post-procedure duplex ultrasound performed (Yes, No)
- Duration between treatment and post-procedure duplex ultrasound
 - $Duration\ (days) = Date\ of\ post-procedure\ duplex\ ultrasound - date\ of\ first\ treatment + 1$
- Occlusion of target/treated vein? (Yes, No, N/A), for those that had a post-procedure duplex
- Compression compliance? (Yes, No)
- Hospitalized for target wound since last contact? (Yes, No)
- If wound previously closed/healed, was there recurrence? (Yes, No, N/A)
- Has previously healed target ulcer reopened? (Yes, No)

3.5 Effectiveness endpoints

3.5.1 Primary endpoint(s)

Summary statistics with 95% CI will be provided for all primary endpoints. The Clopper-Pearson (1934)¹ method will be used for binary proportions (wound closure at 12 weeks post-treatment). Additionally, distribution of time to wound closure will be estimated using the KM method and the 25th percentile, median, and 75th percentile will be presented along with 95% CIs.

3.5.1.1 Rate of epithelial migration (mm/week) by perimeter

Baseline, time point value, change from baseline and percent change from baseline of the wound perimeter will be summarized by visit time points identified in section 3.1.

The wound perimeter will be evaluated for skewness using the Kolmogorov Smirnov test. In the event of significant skewness, the interquartile range will also be reported in addition to the 95% CI.

Additionally, the baseline, time point value, change from baseline and percent change from baseline will be presented for the subset of wounds that healed.

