### 5.3 Primary Endpoint(s)

- Rate of epithelial migration (mm/week) measured by wound perimeter on photograph taken using the DCT and submitted to Tissue Analytics® for analysis
- Wound closure at 12 weeks ( $\pm 1$ wk) post-treatment
- Time from initial treatment with Varithena® to wound closure

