### 10.3 Primary Efficacy Analyses

---

The three primary endpoints are:

- Rate of epithelial migration (mm/week) by perimeter
- Wound closure at 12 weeks post-treatment
- Time to wound closure

Summary statistics with 95% CI will be provided for all primary endpoints. The Clopper-Pearson method will be used for binary proportions (wound closure at 12 weeks post-treatment).

Additionally, distribution of time to wound closure will be estimated using the Kaplan Meier (KM) method and the 25th percentile, median, and 75th percentile will be presented along with 95% CIs.

The primary endpoint, rate of epithelial migration, will be evaluated for skewness using the Kolmogorov Smirnov test. In the event of significant skewness, the interquartile range will be reported in addition to the 95% CI.

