1.3 Study endpoints

The primary endpoints of the study are:

- Rate of epithelial migration (mm/week) measured by wound perimeter on photograph
- Wound closure at 12 weeks (± 1 wk) post-treatment
- Time from initial treatment with Varithena® to wound closure

The secondary endpoints of the study are:

- Percent of wounds remaining closed at 3 months (± 1 wk) post-wound closure date, non-healed wounds are not included in percent calculation
- For healed wounds, rate of VLU recurrence (at same site)
- Change in pain on NPRS compared to baseline at 12 weeks (± 1 wk), 6 months (± 1 wk), 12 months (± 1 wk) post-treatment
- Change on Euroqol five dimension five level questionnaire (EQ-5D-5L) quality of life assessment compared to baseline at 12 weeks (± 1 wk) and 12 months (± 1 wk) post-treatment
- Change in Venous Clinical Severity Score (VCSS) from baseline to 12 week (± 1 wk) and 12 month (± 1 wk) follow-up
- Number of ulcer-free weeks defined as weeks from time of closure (complete epithelialization is recorded) to date of recurrence (at same site) or last contact if no recurrence (at study completion or withdrawal)

2 Changes to protocol analysis

The interim analyses were expanded to look at hospitalization and safety information. Please see section 3.8 for further details.

Additional exploratory analyses from the Wound Health Index (WHI) will not be conducted.

NPRS analyses will use data from both the sDCT and the electronic data capture (EDC). The analysis will be summarized by each week through 12 weeks, 6 months and 12 months post-treatment. Additionally, the categories by severity will not be summarized but rather the numerical scale will be summarized and presented in a shift table. Refer to section 3.5.2 for further details.

Sub-group analyses will not be performed. There is not enough data collected for the analyses to be meaningful.

3 Statistical methods and analysis

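### SAP 3.5.1.1 derives no mm/week rate for the first primary endpoint and does not declare the change; its weekly perimeter tables also lose wounds once they close

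*SAP*

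**What the plan says.** **Endpoint.** Protocol 5.3 lists "Rate of epithelial migration (mm/week) measured by wound perimeter on photograph taken using the DCT" first among the primary endpoints. Protocol 10.3 repeats it, and SAP 1.3 has "Rate of epithelial migration (mm/week) measured by wound perimeter on photograph". SAP 3.5.1 then commits to this: "Summary statistics with 95% CI will be provided for all primary endpoints".

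**Planned analysis.** Under the mm/week title, SAP 3.5.1.1 states: "Baseline, time point value, change from baseline and percent change from baseline of the wound perimeter will be summarized by visit time points". A further table covers healed wounds: "Additionally, the baseline, time point value, change from baseline and percent change from baseline will be presented for the subset of wounds that healed".

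**Skewness.** Protocol 10.3: "The primary endpoint, rate of epithelial migration, will be evaluated for skewness using the Kolmogorov Smirnov test". SAP 3.5.1.1: "The wound perimeter will be evaluated for skewness using the Kolmogorov Smirnov test".

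**Declared changes.** SAP section 2 opens with "The interim analyses were expanded to look at hospitalization and safety information" and goes on to the Wound Health Index, the pain scale and the sub-groups. The migration rate is not mentioned.

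**Images.** Weekly photographs are scheduled until closure (SAP 1.1). Protocol 7.1.3 also asks for the healed area to be photographed at wound-care visits. SAP 4.3 step 2 removes photographs dated after the site's closure date in the EDC, step 4 keeps only reviewed records, and step 5 keeps only evaluable ones. SAP 3.1 takes the largest image in a window. SAP 3.5.1.4 imputes nothing.

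**The concern.** There are two points of unequal weight.

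1. **The rate is missing.** A change in mm is not a rate, and a table of means by visit is not a rate per wound with a 95% CI. Protocol 10.1 leaves the detailed methods to the SAP, so the formula belongs there. If it is chosen after the data are seen, the value of a primary endpoint becomes a free choice.

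2. **Closed wounds leave the tables.** No rule enters 0 mm for a wound after closure. From the next window on, the wound has no scheduled photograph, and any sDCT photograph of the healed area is removed. The rows for later weeks then describe mainly the wounds that have not healed. The healed-subset table uses the same images and has the same loss. Step 2 makes no exception for photographs taken after a recurrence, so a reopened wound is lost as well.

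**Working it through.** **No planned figure to reproduce.** The documents state no expected rate, SD or sample size calculation for this endpoint.

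**Step 1: the texts side by side.**

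| Item | Protocol 5.3 and 10.3 | SAP 3.5.1.1 |
|---|---|---|
| Quantity | rate, mm/week | perimeter, change, percent change |
| Time denominator | implied by the unit | none |
| Skewness test applied to | the rate | the perimeter |
| Declared in SAP section 2 | – | no |

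**Step 2: does the formula matter?** Compare two readings: (i) baseline perimeter minus final perimeter, divided by weeks to closure or to Week 12 if still open; (ii) change to Week 12 divided by 12, with closed wounds at 0 mm. Take an assumed wound of 100 mm that closes at week 6. Reading (i) gives 100/6 = 16.7 mm/week and reading (ii) gives 100/12 = 8.3 mm/week.

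A simulation of 400,000 circular wounds shows the effect on the summary. Assumed inputs: median radius 15 mm with log-SD 0.5; constant edge speed, lognormal with CV 0.8, scaled to a chosen share closed by Week 12; no measurement error; EDC closure date equal to true closure.

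| Closed by Week 12 | Mean (i) | Mean (ii) | Ratio of means | Ratio of medians |
|---|---|---|---|---|
| 40% | 8.06 | 5.63 | 1.43 | 1.24 |
| 60% | 12.49 | 6.86 | 1.82 | 1.57 |

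**Step 3: percent change in the weekly tables.** Let c be the share closed and m the mean percent change among open wounds. With closed wounds at 0 mm, which is -100%:

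all-wound mean = -100c + (1 - c) × m

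For an assumed m = -40%:
- c = 0.20: -20 - 32 = -52%
- c = 0.40: -40 - 24 = -64%
- c = 0.62: -62 - 15.2 = -77.2%

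The value 0.62 is the 12-week healing share (13/21) of the control group in one earlier foam sclerotherapy trial described in Protocol 4.1. It serves only as an illustration.

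A photograph on the closure date itself survives step 2. The simulation in step 2 keeps that closing-week zero and still gives, at Week 11, -54.1% as written against -68.8% with closed wounds at 0 mm (40% closed by Week 12), and -62.1% against -81.7% (60%).

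**Step 4: reopened wounds.** If a fraction f of closed wounds has reopened to baseline size, the closed group averages -100(1 - f)%. The understatement reverses when f exceeds 1 + m/100: above 0.60 for m = -40%, above 0.20 for m = -80%.

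**Step 5: change in mm.** A second simulation (median perimeter 100 mm, median edge advance 0.9 mm/week, both assumed) compares open wounds with all wounds after 12 weeks, with 29% closed:
- sizes vary, speeds similar: -67.8 mm open against -61.6 mm all, so shrinkage is overstated;
- speeds vary, sizes similar: -54.1 mm open against -67.3 mm all, so it is understated.

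The documents give neither distribution, so the direction cannot be fixed in advance.

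**Step 6: which windows.** The weekly images to Week 11 and the 6-month image are taken by the subject in the sDCT, so step 2 reaches them. The Week 12 image is taken in clinic and entered in the iDCT, for healed wounds too (Protocol 8.1.5). SAP 4.3 is titled for sDCT data and does not say whether its steps cover iDCT images. In the step 2 simulation at 40% closed, the Week 12 mean is -51.9% if healed-area clinic images are removed and -70.2% if they stay, against -71.6% at day 84.

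**The case against.** **The tables already give a rate.** Windows are weekly, so dividing a mean change by its week number gives mm/week. That stands only as a crude figure. It is not a rate per wound, no CI for it is planned, and it carries the loss of closed wounds.

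**The table shells may hold a formula.** They are a separate document that was not seen. A reader might infer that the sponsor has dropped the endpoint. The documents do not show that; the claim concerns the SAP text. The protocol gives no formula either.

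**Percent shrinkage is always understated.** This reading is tempting because -100% is the largest possible reduction. It holds for wounds that stay closed, relative to counting them at 0 mm. Enough reopened wounds could reverse it.

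**Step 2 is the cause.** Only in part. The photograph schedule itself ends at closure, so much of the loss would occur without step 2.

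**The Week 12 row is biased, or is safe.** Neither can be asserted. It depends on whether steps 2, 4 and 5 apply to iDCT images.

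**The sizes are invented.** Every simulated figure rests on assumed inputs and on formulas that are not in the documents. If sites date closure late while subjects keep photographing the healed area, more zeros survive and the gap shrinks. This objection stands: the figures show that the choice matters, not how large the bias will be.

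**The study is descriptive.** True, and no hypothesis test is at risk. But in a descriptive registry the estimates are the result.

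**Conclusion.** The main point holds on the text alone. One of three primary endpoints has no derivation in the SAP, its skewness test has moved to another variable, and neither change is declared. This must be fixed before the data are analysed.

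The secondary point also holds, at lower severity. Closed wounds leave the weekly and healed-subset perimeter tables, clearly so in the sDCT windows (to Week 11, and 6 months). Against counting closed wounds at 0 mm, mean percent shrinkage is understated for wounds that stay closed, by an amount that depends on the share closed. The direction in mm is unknown, and the Week 12 row is undetermined.

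A reader might extend this to the other two primary endpoints. The documents do not support that: 12-week closure is taken from EDC status (SAP 3.5.1.2), and time to closure is a Kaplan-Meier analysis with open wounds censored (SAP 3.5.1.3). Neither uses the perimeter tables.

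**What to change.** **Rate (SAP 3.5.1.1).** Derive one value per target wound:

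rate = (baseline perimeter - perimeter at t) / (weeks from baseline image to t)

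If the wound closed by the Week 12 visit, t is the EDC closure date and the perimeter is 0. Otherwise t is the last evaluable image up to that visit. State that this measures perimeter reduction per week, not linear edge advance: 1 mm of advance removes 2π = 6.28 mm of perimeter from a circle. Report the mean with 95% CI, the median and the IQR. Apply the skewness test to the rate, as in Protocol 10.3. Report the number of wounds without a rate.

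**Tables.** Count closed wounds at 0 mm from the EDC closure date until any recorded recurrence, and keep images taken after a recurrence. Do the same in the healed-subset table. Keep the open-wound-only table as supportive.

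**Image rules.** State whether SAP 4.3 steps 2, 4 and 5 cover iDCT images, and how the largest-image rule works in a window that contains closure.

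**Declaration.** List the rate formula and the 0 mm rule in SAP section 2. Say there that the 0 mm value comes from EDC closure status and not from a photograph, since both documents rule out imputation.

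**Cost.** SAP wording and a little programming. Perimeters, image dates and EDC closure dates are already planned. The downside is that the rate depends on how accurately sites date closure, and very early closures give large rates, so the median and IQR should be read with the mean.

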Statistical Methods	
Wound area and perimeter will be measured at baseline and each week up to 12 weeks in order to assess rate of epithelial migration, wound closure at 12 weeks and time to wound closure.
 
Secondary endpoints, VCSS, NPRS, and EQ-5D-5L will be calculated as difference from baseline at each visit. Recurrence will be defined as wounds that were reported to have closed, but did not remain so.
 
Summary statistics of the primary and secondary endpoints will be reported with 95% confidence intervals (CI). CIs will be estimated using the Kaplan-Meier method for time to event analyses and the exact (e.g., Clopper-Pearson) method for binomial proportion analyses.
 
Additionally, distribution of continuous endpoints will be evaluated for skewness. Missing data will not be imputed.

Registry Procedures	See Table 1: Schedule of Registry Assessments below
Data Collection	
All Investigator and subject data is collected via a DCT. There are two versions of the DCT: physician-facing, referred to as Investigator data capture tool (iDCT), and subject-facing, referred to as subject data capture tool (sDCT). Investigator data can be entered into the iDCT through an application downloaded on a Sponsor-provided tablet or by using the web portal. Subjects collect wound photographs and answer an NPRS question on a Sponsor-provided tablet via the sDCT at designated time points. This allows for photograph and data collection between clinic visits.
 
Data is maintained in a Health Insurance Portability and Accountability Act (HIPAA) compliant database. Subject data is linked to Investigator data by the subject identification code (SIC).

Central Imaging	All wound photographs collected for this registry are submitted via the iDCT and sDCT. Tissue Analytics® analyzes each photograph, or set of photographs for circumferential wounds, and provides wound color and size data for statistical analyses.

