3.6 Additional Efficacy Analyses

A univariable cox regression model will be presented for the time to wound closure investigating effects of the following factors in a one at a time analysis: patient age, wound age at first encounter (weeks), presence of infection, ambulatory method, wound size at baseline and total wounds/ulcers of any type. The hazard ratio, 95% CI and the p-value will be summarized for each factor. All factors in the univariable models with a two-sided p-value <0.15 will be included in a multivariable analysis to determine the impact of these factors.

The overall VAS and change from baseline will be presented by summary statistics with 95% CI. Additionally, the EQ-5D-5L misery score will be calculated and summarized similarly to the VAS and index health state score. This is calculated by adding the dimensions together. As an example, if the health state is 11111, then misery score would be 5.

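### SAP 3.5.1.1 never derives the mm/week migration rate that it names: it tabulates cumulative perimeter change, which is not edge advance, and uses no wound area

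*SAP*

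**What the plan says.** Protocol 5.3 defines the first of three primary endpoints as "Rate of epithelial migration (mm/week) measured by wound perimeter on photograph taken using the DCT", with no formula. Protocol 10.3 and SAP 1.3 repeat the name and unit, also without a formula.

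The Statistical Methods entry of the protocol synopsis names two inputs: "Wound area and perimeter will be measured at baseline and each week up to 12 weeks in order to assess rate of epithelial migration". Under central imaging, the vendor "provides wound color and size data for statistical analyses".

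SAP 3.5.1.1 keeps the mm/week heading, but its content is the perimeter at baseline and at each visit, and then "change from baseline and percent change from baseline of the wound perimeter will be summarized by visit time points". The same summaries are repeated for wounds that healed. Protocol 10.3 applies the Kolmogorov-Smirnov check to the rate; SAP 3.5.1.1 applies it to the perimeter.

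Area is not summarised anywhere in the SAP. The only other size variable is a Cox model covariate in SAP 3.6, listed as "wound size at baseline and total wounds/ulcers of any type", without saying whether size means area or perimeter. The protocol's area subgroups (10.6) go with all other subgroups, which SAP section 2 does declare: "Sub-group analyses will not be performed". Section 2 does not mention the missing rate or the absence of area from this endpoint.

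**The concern.** A rate in mm/week needs a distance and a time. SAP 3.5.1.1 supplies neither. The tabulated change accumulates from baseline, so it grows with follow-up even when healing is steady. It is also a change in the length of an outline, whereas migration in mm is most naturally read as how far the edge moves inward.

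The registry tests no hypothesis (SAP 1.1.1), so its estimates are its product. A primary endpoint with a rate label and no rate cannot be reported as specified. Leaving the formula open also allows it to be chosen after the data have been seen. Protocol 10.5 foresees comparing outcomes with historical wound-registry data; if this endpoint were included, the quantity and unit would have to be defined first.

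**Working it through.** The documents state no migration figure, so there is nothing to reproduce. The check is plane geometry on assumed shapes. P is perimeter, A is area, and 0 and 1 mark the earlier and later image. Mean edge advance is taken as d = (A0 - A1) / [(P0 + P1)/2].

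**1. Uniform inward advance of 1 mm**
- Circle, radius 20 to 19 mm: perimeter loss = 2π × 20 - 2π × 19 = 6.28 mm.
- Ellipses with semi-axes 30 × 20 and 40 × 20 mm: 6.28 mm each. This is one geometric identity (2πd for a smooth convex outline and a small offset), not separate confirmations.
- Rectangle 60 × 20 mm: P0 = 160, P1 = 2 × (58 + 18) = 152; loss 8 mm.
- In each case d returns 1.00 mm for this small step.

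**2. Other healing patterns (perimeter loss per mm of mean advance)**
- Shrinkage at constant shape: the ratio is P²/(2A). Circle 6.3; ellipses 2:1, 3:1 and 4:1 give 7.5, 9.5 and 11.7; square 4²/(2 × 1) = 8.0; 3:1 rectangle 8²/(2 × 3) = 10.7.
- Only the long edges of a 60 × 20 mm rectangle advance by 1 mm each: P falls from 160 to 156 and A from 1200 to 1080; d = 120/158 = 0.76; ratio 4/0.76 = 5.3.
- Range over the assumed cases: about 5 to 12.

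**3. What the SAP would tabulate.** With a smooth outline and a steady true advance of 1 mm/week, the change from baseline is 2π × weeks: 6.3 mm at week 1, 25.1 mm at week 4 and 75.4 mm at week 12. The rate is 1 mm/week throughout.

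**4. Percent change does not help.** For circles of radius 15, 20 and 40 mm, the same 12 mm of advance is a perimeter loss of 12/15 = 80%, 12/20 = 60% and 12/40 = 30%. It mixes migration with starting size.

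**5. Limits of an area-based formula.** In one step from baseline to closure, A1 = P1 = 0 and d becomes 2A0/P0. True advance is the half-width.
- 40 × 20 mm ellipse: 2 × 628.3/96.9 = 12.97 against 10; ratio 1.30.
- 60 × 24 mm ellipse: 2 × 1131.0/138.1 = 16.38 against 12; ratio 1.37.
- 40 × 20 mm rectangle: 2 × 800/120 = 13.33 against 10; ratio 1.33.
- Circle: 1.00.

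Summing over weekly images reduces this. For the 40 × 20 mm rectangle closing at 1 mm/week, the first nine steps each give 1.00. The last step, from 22 × 2 mm (A = 44, P = 48), gives 44/24 = 1.83. The sum is 10.83 over 10 weeks, or 1.08 mm/week, instead of 1.33.

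**The case against.** The perimeter basis is the protocol's own, so the SAP did not invent it, and the documents never define migration as inward edge advance. That reading rests on the name and the unit. This stands. It makes the perimeter part of the problem one of definition, shared by both documents. It does not supply the missing rate, and it does not account for the area that the synopsis names.

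A reader might infer that the plan will overstate the migration rate roughly six-fold. The documents do not support that. The SAP computes no mm/week figure, so there is no printed rate to be overstated. The factor of 6.3 would apply only if someone divided perimeter change by weeks and read the result as edge advance, and even then it depends on shape and healing pattern.

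A reader might also infer that area is indispensable, or that it is no longer collected. Neither follows. For a smooth, uniformly closing wound, perimeter change divided by 2π gives the advance without area; area is needed so that the estimate does not lean on shape. The protocol still has area measured; only its analysis is absent. Nor is the area-based formula exact in general, as step 5 shows.

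The table shells are a separate document and might hold a derivation, but a primary endpoint's formula belongs in the SAP. Finally, no test or sample size depends on this endpoint, and the other two primary endpoints (closure at 12 weeks and time to closure) are unaffected. That limits the damage but leaves the first endpoint unreported as defined.

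**Conclusion.** The point holds. Followed as written, SAP 3.5.1.1 reports cumulative perimeter change under the name of a weekly migration rate, uses no area, and SAP section 2 declares neither change. This is more than missing detail, because the planned quantity differs from the named one.

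The gap between perimeter loss and edge advance is about 6.3 mm per mm for a smooth, uniformly closing wound and about 5 to 12 across the assumed cases. These ratios rest on assumed shapes and healing patterns and on reading migration as inward edge movement. They show that the two quantities are not interchangeable; they do not estimate a bias in any planned result. The absence of a rate and of area rests on the text alone.

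**What to change.** In SAP 3.5.1.1, define a per-wound rate in mm/week. One option is to compute area change divided by mean perimeter for each pair of consecutive images, sum these, and divide by the weeks elapsed between actual dates. For healed wounds, stop the clock at the closure date and set area and perimeter to zero there. This needs stating because SAP 4.3 removes photographs taken after site-recorded closure, and because a fixed end date would shrink a healed wound's rate with every week after closure. Working image by image limits the upward error of about 1.3 to 1.4 times that a single baseline-to-closure step gives for elongated wounds.

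Report the rate with a 95% CI and apply the skewness check to it. Keep perimeter change as a separately labelled descriptive measure, add an area summary, align the protocol endpoint wording, and list the change in SAP section 2. At minimum, relabel the tabulated quantity as perimeter change and declare that the rate is not derived.

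The cost is SAP wording, one derived variable from measurements the protocol already requires, and a little more programming. The printed figure will be smaller than a perimeter change.
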